- Our hypothesis is that NGT is well tolerated during HFNC without serious adverse events. We hypothesize that there will be no difference in length of HFNC therapy, number of emesis, peak respiratory support between patients receiving NGT compared to NDT. We also hypothesize that there will be no difference in these outcomes in the subgroup of high risk population: premature infants, neurological disorders, gastroesophageal reflux patients.

Objectives

- The primary objective is to compare length of respiratory support, number of emesis documented by nursing, peak respiratory support (flow of HFNC, or y/n on CPAP/MV), and ER revisit/hospitalization rates between the gastric feeding group and the post pyloric feeding group

- The secondary objective is to perform an analysis of the highest risk population: premature (born < 37 weeks gestation), neuromuscular disorders, seizures, cerebral palsy, EOE, upper airway disorders – laryngo/tracheomalacia, hemodynamically unstable heart disease, medically managed GERD; and compare the same outcomes between NGT and NDT feedings in this group compared to the low risk group (>37 weeks gestation with none of the above comorbidities).

Study Design

- Design will be a randomized controlled trial.
- Stratified Block Randomization will be done for both high risk population and low risk population through REDCap.
- Duration of study will be until calculated sample size is reached. Subjects will be followed during their acute hospitalization and then followed up by phone interview 7 days and 30 days after discharge
- The primary outcome is total length respiratory support. If HFNC causes increased rates of reflux and subsequent aspiration, we expect length of therapy to be increased in NGT group compared to the NDT group.
- Our secondary outcomes include number of emesis, peak respiratory support, number of x-rays obtained, length of stay, and ER revisit and hospital readmission rates.
- Safety assessments by clinicians will be done daily by primary physician based off of standardized criteria of number of emesis in conjunction with need for increased respiratory support to determine if feeds should be held or not. Patients that transferred to the PICU will be an outcome we track however this study will not dictate ICU feeding management.
- No blinding for study authors involved as they are attending physicians caring for the infants

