- Data will be blinded for the statistician and the investigator making follow up phone calls

Study Population

- Inclusion criteria: All admitted patients less than 12 months old for bronchiolitis requiring high flow nasal cannula therapy at Children's Memorial Hermann.
- Exclusion criteria: Patients with craniofacial abnormalities that prevent tube placement. Patients with prior surgery compromising esophageal sphincter tone such as Nissen fundoplication or congenital hiatal hernia surgery are excluded. Patients requiring CPAP and mechanical ventilation are also excluded from the study.
- Recruitment strategy: When patients are either started on HFNC on the inpatient floor or transferred from the emergency room on HFNC without enteral nutrition, caretakers will be asked to consent to the study by the study investigators when the primary physicians have made the clinical decision to start tube feedings.

Study Procedures

- Once consented, patients will be randomized into a NGT or NDT group – via stratified block randomization module on UTH REDCap
- Chest X-ray will be obtained to confirm placement of tube before feeding is initiated
- Feeds will be initiated in a standardized rate and volume
- Patients will be continued to be fed according to randomization until HFNC is discontinued.
- Caretakers can withdraw patients from study at any point
- Primary physicians can withdraw patient from study at any point if they are concerned about adverse events

- Bronchiolitis and HFNC will be managed per standard bronchiolitis protocol
- Continued admission and subsequent discharge will be determined by primary physician
- Information to be gathered includes demographic information (age, sex, race, weight), historical information (birth history, past medical, family history), and information about the course of the admission (length of stay, number of emesis, number of x rays performed, antibiotics used, peak respiratory support, number of revisits to ER and rehospitalizations)
- Data will be collected through chart review in EMR as well as phone follow up interview 7 days and 30 days after discharge by blinded investigators

Data and Safety Monitoring

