All analyses will be intent-to-treat. Differences in length of HFNC therapy between treatment groups will be assessed with a regression model including treatment and risk group (stratifying variable) as covariates. Rates of secondary outcomes will be assessed using log binomial or logistic models, and total number of secondary outcomes will be assessed with negative binomial models. In this small pilot study, some treatment effects that would be considered important by family members and clinicians (reduced hospital days) may not be statistically significant. As a result, Bayesian analyses will also be performed to estimate the probability of benefit. Neutral, weakly informative priors will

be used for the treatment effect, e.g. for binary outcomes, the prior relative risk will be centered at 1.0 with 95% prior interval of 0.5-2.0.

Ethics

- IRB approval will be sought from CPHS
- Consent will be obtained prior to any enrollment into the trial.
- A consent form will be printed and handed to each patient describing the purpose of the trial and the risks involved

Data handling and record keeping

- Data will be stored on UTShare account and requiring 2 step authentication and PHI protected as well as the UT Houston REDCap.
- There will be no paper records
- Data will be kept until ten years after completion of study

Quality control and assurance

- Self assessments will be made to check that data collected were for patients admitted for bronchiolitis and the other inclusion criteria

Publication Plan

- Dissemination of knowledge from this study by resident education, nursing education, abstract and poster presentation leading to medical journal publication

CITATIONS

2. Shepherd, Kelly, David Hillman, and Peter Eastwood. "Symptoms of Aerophagia Are Common in Patients on Continuous Positive Airway Pressure Therapy and Are Related to the Presence of Nighttime Gastroesophageal Reflux." *Journal of Clinical Sleep Medicine* (2013)

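### The declared primary outcome is total length of respiratory support, but the only duration model and the sample size use length of HFNC; the two are never defined or equated and can differ in infants who escalate.

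*Combined protocol and SAP*

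**What the plan says.** Study Design names the outcome: "The primary outcome is total length respiratory support". Objectives agrees: "The primary objective is to compare length of respiratory support". The Bayesian continuation rule under Statistics, which applies if recruitment falls short after two respiratory seasons, is also framed on respiratory support duration.

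Three other places use HFNC. The hypothesis at the end of Background Information concerns length of HFNC therapy. The sample size under Statistics uses retrospective means and SDs of HFNC hours and a 24-hour difference in HFNC duration. The Statistical Analysis Plan states: "Differences in length of HFNC therapy between treatment groups will be assessed with a regression model", with treatment and risk group as covariates.

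On escalation, Objectives lists "peak respiratory support (flow of HFNC, or y/n on CPAP/MV" as an outcome, and Study Design adds: "Patients that transferred to the PICU will be an outcome we track". Study Population says: "Patients requiring CPAP and mechanical ventilation are also excluded from the study", without giving a time. Statistics keeps every randomised infant in the analysis, and the Statistical Analysis Plan is intent-to-treat.

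**The concern.** For an infant who goes from HFNC to room air without escalating, the two durations can be the same number. For an infant who moves to CPAP or a ventilator they need not be, and the plan does not say how those hours count. One statistician following Study Design and another following the Statistical Analysis Plan could compute different primary variables from the same charts, and nothing in the plan settles which is right before the data are seen.

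The difference falls where the protocol looks for harm. Study Design reasons that if HFNC promotes reflux and aspiration, "we expect length of therapy to be increased in NGT group compared to the NDT group". An infant who aspirates and escalates early could have a short HFNC time. Counting HFNC alone would then score a bad course as a short one, and an arm that escalates more could look better than it is.

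Two further consequences follow. The stated power belongs to HFNC hours. And if the continuation rule is used, enrolment would be governed by one variable and the final test by the other.

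**Working it through.** **1. Which variable each part uses**

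| Place | Variable |
|---|---|
| Study Design, primary outcome | total respiratory support |
| Objectives | respiratory support |
| Statistics, Bayesian rule | respiratory support |
| Background Information, hypothesis | HFNC |
| Statistics, sample size | HFNC |
| Statistical Analysis Plan, regression | HFNC |

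No section defines either term or sets them equal.

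**2. The plan's own sample size.** Inputs from Statistics: difference 24 h; SD 29.5 h (low risk) and 40.06 h (high risk); alpha 0.05; 'B of 0.8' read as power 0.80. Two-sided testing is assumed; equal arms are stated under Data and Safety Monitoring. Normal approximation: n per arm = 2 × (SD × 2.80 / 24)².

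- Low risk: 23.7, so 24 per arm and 48 in total (power 0.805).
- High risk: 43.7, so 44 per arm and 88 in total (power 0.802).

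Both match exactly. The arithmetic is right, and it is tied to HFNC hours.

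**3. The pooled regression on HFNC hours.** Total 48 + 88 = 136, or 68 per arm.

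- Pooled SD = √[(48 × 29.5² + 88 × 40.06²) / 136] = 36.7 h.
- SE = 36.7 × √(2/68) = 6.29 h; 95% CI half-width 1.96 × 6.29 = 12.3 h.
- Power for 24 h is about 0.97. It stays at or above 0.80 until the SD is 24 / (2.80 × 6.29) = 1.36 times larger, about 50.0 h.

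**4. Power for total support, on assumed inputs.** The documents give no SD for total support, no escalation rate and no CPAP or ventilation hours. Assume a proportion p of 5% or 10% escalates and adds hours with mean m and SD s of 48 and 24, or 96 and 48, independent of HFNC hours. The added variance is p(m² + s²) − (pm)².

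| p | m, s (h) | Added variance | Pooled SD (ratio) | Pooled power | Low-risk power | High-risk power |
|---|---|---|---|---|---|---|
| 5% | 48, 24 | 138.2 | 38.5 (1.05) | 0.95 | 0.745 | 0.77 |
| 10% | 48, 24 | 265.0 | 40.1 (1.09) | 0.94 | 0.69 | 0.74 |
| 5% | 96, 48 | 553.0 | 43.6 (1.19) | 0.89 | 0.60 | 0.68 |
| 10% | 96, 48 | 1059.8 | 49.0 (1.34) | 0.81 | 0.47 | 0.59 |

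Power is for a true 24 h difference at 68 per arm (pooled), 24 per arm (low risk) and 44 per arm (high risk).

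**5. What an HFNC-only count could leave out.** Suppose none of the CPAP or ventilation hours is counted and the mean hours per escalated infant are equal in the two arms. The missing between-arm difference is then the excess escalation times those hours. For an assumed excess of 5 to 10 percentage points and 48 to 96 h, this runs from 0.05 × 48 = 2.4 h to 0.10 × 96 = 9.6 h, against a 24 h target and a half-width of 12.3 h.

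**The case against.** The strongest reply is that one variable was meant throughout. The hypothesis lists HFNC length, emesis and peak support. The objective opens with the same list but puts respiratory support length in first place. On this reading the fault is loose naming. That is plausible, but no section says so, and the outcome in Objectives counts CPAP and ventilation as respiratory support that is not HFNC.

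A reader might infer that CPAP and ventilation hours are certainly lost from the primary analysis. The documents do not support that, because length of HFNC is itself undefined. The hours drop out if HFNC time is summed by mode, or if the infant never returns to HFNC. A clock from first start to final stop would include them for infants who step back down.

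It may also be said that infants needing CPAP or ventilation are excluded, so the two durations coincide. The exclusion carries no timing. Reading it as removal after randomisation conflicts with intent-to-treat, with CPAP/MV as an outcome and with tracking PICU transfers. Exclusion at entry is the natural reading, though still a reading.

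Finally, escalation is not invisible: CPAP/MV, PICU transfer and length of stay are all recorded. That stands, but none of them puts the hours into the primary comparison.

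**Conclusion.** The mismatch is explicit and nothing in the plan resolves it. Taken literally, and with the CPAP/MV exclusion read as an entry criterion, the only duration model tests a variable other than the declared primary outcome in infants who escalate. Confidence is high for the mismatch and moderate for omitted CPAP and ventilation hours, which depend on how HFNC length is measured.

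The bias is possible, not shown. Its size cannot be found from the documents; the 2.4 to 9.6 h range rests on assumed rates and hours and on full omission.

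A reader might infer that analysing total support would leave the trial badly underpowered. Under the 5-10% escalation assumed here, the pooled regression keeps power of about 0.81 or more. Within strata, the basis on which 48 and 88 were set, power would fall from 0.80 to between about 0.74 and 0.47 (low risk) and between about 0.77 and 0.59 (high risk).

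**What to change.** - **Statistical Analysis Plan:** make the dependent variable of the primary regression the declared outcome, total hours of respiratory support counting HFNC, CPAP and mechanical ventilation. Keep treatment and risk group as covariates, and keep HFNC-only hours as a supportive analysis.
- **Statistics:** use the same variable in the Bayesian continuation rule.
- **Clock:** count hours from randomisation, because infants are already on HFNC when families are approached and earlier hours cannot reflect the assigned tube. State the stop time, including whether low-flow oxygen after HFNC counts.
- **Data:** take start and stop times for each mode from the review already planned: "Data will be collected through chart review in EMR".
- **Power statement:** say that 48, 88 and 80% power were derived for HFNC hours and are not established for total support. Restate power from the retrospective admissions if the mode times exist there, without enlarging the trial.

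The cost is wording and some extra chart abstraction, with no extra patients. The downside is that total support may be more variable, so power may be somewhat lower than stated.

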- Adverse events including reflux and subsequent aspiration are theoretically possible and the purpose of this study. There have been several studies involving nutrition in bronchiolitis that have shown NGT feedings to be safe (3,4,5). If the clinician believes that aspiration/reflux is the cause of worsening respiratory distress and respiratory support, the mode of feeding can be changed if deemed necessary by treating physician.
- A review will be conducted by the safety coordinator of the research team at the 50% enrollment mark. Because this is a randomized control trial with equal groups, a standardized normal deviate test as described in <https://www.ncbi.nlm.nih.gov/pmc/articles/PMC1471979/> will be calculated at this time. The cumulative results of adverse events will be used with $p < 0.05$ as the level of significance. If it is shown that there is increased aspiration and this arm is not safe, the trial and study will end.

Statistics

- Statistical analysis will be performed by UT Houston statistician or through CCTS
- Based on retrospective data of bronchiolitis admissions over the past 3 years, the average length of HFNC for low risk infants were 83.3 hours with a standard deviation of 29.5. The average length of HFNC for high risk infants were 87.75 with a standard deviation of 40.06. Assuming B of 0.8 and alpha of 0.05, an N of 48 and 88 were calculated to detect a difference of 24 hours in the duration of HFNC in the low and high risk group respectively.
- $p < 0.05$ to be used for level of significance
- All randomized subjects will be included in the analysis. Subsequent subgroup analysis will be performed on gestational age at birth, weight at study entry, birth weight, mode of delivery PMH by organ system, viral organism, and level of respiratory support.
- In the case that the calculated sample size is not reached by the end of the second respiratory season, enrollment will continue until Bayesian analysis performed annually for up to 2 years identifies 90% or greater probability that there is a difference of respiratory support duration between the two groups or until planned sample size is met.

Statistical Analysis Plan

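### The trial is sized separately in each risk stratum and compares the strata as its secondary objective, but the SAP's HFNC-duration model states no stratum estimate or between-stratum contrast

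*Combined protocol and SAP*

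**What the plan says.** Four parts of the document treat risk group as a unit of inference.

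- **Background Information:** "We also hypothesize that there will be no difference in these outcomes in the subgroup of high risk population".
- **Objectives:** the secondary objective is to "compare the same outcomes between NGT and NDT feedings in this group compared to the low risk group".
- **Study Design:** "Stratified Block Randomization will be done for both high risk population and low risk population through REDCap".
- **Statistics:** each risk group has its own SD (29.5 h low risk, 40.06 h high risk), and "an N of 48 and 88 were calculated to detect a difference of 24 hours in the duration of HFNC", one for each risk group.

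The **Statistical Analysis Plan** then gives HFNC duration one model, "a regression model including treatment and risk group (stratifying variable) as covariates". It mentions no treatment-by-risk term, no estimate within a stratum and no contrast between strata. The log binomial, logistic and negative binomial models for the secondary outcomes are named without covariates.

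Elsewhere in Statistics, the subgroup sentence reads "Subsequent subgroup analysis will be performed on gestational age at birth, weight at study entry, birth weight, mode of delivery PMH by organ system" and goes on to viral organism and level of respiratory support. It does not name the randomised high/low-risk grouping. The Bayesian rule for continuing enrolment concerns a single comparison of the two feeding groups.

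**The concern.** The contrasts that set the sample size, and the contrast that forms the secondary objective, have no analysis written for them. A model with treatment and risk group as main effects lets the strata differ in mean HFNC duration but forces the effect of feeding route to be the same in both. If the routes differ mainly in high-risk infants, the group the protocol singles out, the common estimate understates the difference there and overstates it in low-risk infants.

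The estimator, its variance and any handling of multiplicity for the stratum results would then be chosen after the data are seen. The planned 80% power would also describe contrasts that the SAP does not contain.

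**Working it through.** **Inputs (Statistics section).** SD 29.5 h (low risk) and 40.06 h (high risk); target difference 24 h; alpha 0.05; the stated 0.8 read as power; equal arms; N of 48 and 88. Sidedness is not stated. Two-sided reproduces the stated N; one-sided gives 38 and 70 and does not. Normal approximation unless noted.

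**1. Reproduce the plan's N.** n per arm = 2 × (1.96 + 0.8416)² × (SD/24)².
- Low risk: 23.7, rounded up to 24 per arm, 48 in total.
- High risk: 43.7, rounded up to 44 per arm, 88 in total.

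Both match exactly, so these are two stand-alone comparisons of the feeding routes.

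**2. Precision within each stratum.** SE = 2 × SD/√N.
- Low risk: 2 × 29.5/√48 = 8.52 h.
- High risk: 2 × 40.06/√88 = 8.54 h.

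The 95% half-width is about 1.96 × 8.5 = 16.7 h in each. Power at 24 h is 80.5% and 80.2% (t-test 78.8% and 79.3%).

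**3. What the main-effects model estimates.** With equal arms in each stratum, the common effect weights the strata by size: 48/136 = 0.353 low and 88/136 = 0.647 high.

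SE = √(0.353² × 8.52² + 0.647² × 8.54²) = 6.29 h. Power for a common 24 h effect = Φ(24/6.29 − 1.96) = 0.968.

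**4. If the effect differs by stratum.** The documents give no figure for this. As an assumption, take 24 h in high-risk infants and a range in low-risk infants:

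| Low-risk effect | Average common estimate | Power | Simulated power |
|---|---|---|---|
| 0 h | 0.647 × 24 = 15.5 h | 69% | 68% |
| 6 h | 15.53 + 0.353 × 6 = 17.6 h | 80% | 80% |
| 12 h | 15.53 + 0.353 × 12 = 19.8 h | 88% | 88% |

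The simulation used the main-effects regression with normal data, the planning SDs and 40,000 runs per case. It gave a type I error of 5.1% under no effect and 96.5% power for a common 24 h.

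In the 0 h case the common estimate lies 24 − 15.53 = 8.47 h below the high-risk effect. Its 95% CI would include 24 h with probability Φ(1.96 − 8.47/6.29) − Φ(−1.96 − 8.47/6.29) = 0.73. It would include the true low-risk value of zero with probability 1 − 0.694 = 0.31.

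**5. The between-stratum difference.** SE = √(8.52² + 8.54²) = 12.06 h; 95% half-width 23.6 h; power about 51% for a 24 h difference between the two stratum effects.

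**6. Why the variance must be stated.** One pooled residual variance gives SD = √[(48 × 29.5² + 88 × 40.06²)/136] = 36.7 h. The stratum SEs become 36.7 × √(2/24) = 10.6 h (low) and 36.7 × √(2/44) = 7.8 h (high), against about 8.5 h each with stratum-specific variances.

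**7. Multiplicity.** Testing both strata at 0.05 gives 1 − 0.95² = 9.75% chance of at least one false positive if neither has an effect.

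**The case against.** The strongest reply is that this is one short combined document. The Objectives promise the risk-group analysis, Statistics gives each stratum its SD, N and target, and only a sentence of model form is missing. The SAP says which covariates are included and does not exclude an interaction. Gestational age and past history by organ system, both in the subgroup list, overlap the high-risk definition. The secondary objective could also mean results set side by side rather than a formal contrast, which the trial was not sized for and would estimate poorly. The protocol's own hypothesis is no difference, overall or in high-risk infants.

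Several of these points stand. Main effects only is an inference, the unequal-effect figures are illustrative, the contrast is imprecise, and any pooled estimate averages over strata.

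They do not close the gap. An objective does not fix an estimator, a variance or the handling of multiplicity. Components of the risk definition are not the randomised grouping, and no method is given for them. If an interaction was intended, it still has to be written down. The wording of the secondary objective sets one risk group against the other, which supports reporting the difference as an estimate with a CI, without claiming a powered test.

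**Conclusion.** The concern holds. The stated HFNC-duration model is valid for the overall question and the stated N is correct, but the model does not answer the secondary objective or the high-risk hypothesis. The 80% belongs to the two within-stratum comparisons. The model as written has about 97% power for a common 24 h effect, and it averages about 15.5 to 19.8 h if the effect is 24 h in high-risk infants and 0 to 12 h in low-risk infants.

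These figures assume the planning SDs in both arms, full enrolment at 48 and 88, equal allocation within strata and the main-effects reading. They apply to HFNC duration only. Study Design says "The primary outcome is total length respiratory support", and the documents give no SD for that measure.

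**What to change.** Keep the risk-adjusted model for the overall effect on HFNC duration, and add to the SAP:

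- **Stratum estimates:** the NGT-NDT difference with a 95% CI in each risk stratum, using stratum-specific or robust variances because the planning SDs differ.
- **Between-stratum difference:** an estimate with a 95% CI, labelled as imprecise (about ±23.6 h at the planned N).
- **Secondary-outcome models:** the randomised risk group as a covariate in the binomial and negative binomial models, with stratum estimates only where event counts allow.
- **Power statement:** the 80% refers to the within-stratum comparisons, and the overall model has about 97% power for a common 24 h effect. Limit this to HFNC duration.
- **Status:** the stratum results are secondary estimates with CIs, given the 9.75% error rate if both are tested at 0.05.

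The cost is SAP wording. No patients or data are added, because randomisation is already stratified by risk. The drawbacks are that wide intervals must be disclosed (about ±16.7 h within strata), and that log binomial fits within a stratum may be unstable for uncommon events with about 24 low-risk infants per arm.

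### The primary regression is valid but adjusts only for risk group; prespecifying age at randomisation, and perhaps weight, could improve precision cheaply if they predict HFNC duration

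*Combined protocol and SAP*

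**What the plan says.** The Statistical Analysis Plan section specifies "a regression model including treatment and risk group (stratifying variable) as covariates" for length of HFNC therapy and names no other covariate. It does not say whether the regression is linear.

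Study Procedures lists "demographic information (age, sex, race, weight" among the data to be gathered. The Statistics section plans subgroup analyses by "gestational age at birth, weight at study entry, birth weight, mode of delivery PMH by organ system", among other factors. Entry weight therefore has a role as a subgroup variable but not as a covariate, and age at entry has no stated role in any analysis.

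The sample size in the Statistics section rests on unadjusted standard deviations: "the average length of HFNC for low risk infants were 83.3 hours with a standard deviation of 29.5", and "The average length of HFNC for high risk infants were 87.75 with a standard deviation of 40.06". From these, "an N of 48 and 88 were calculated to detect a difference of 24 hours in the duration of HFNC", for the low-risk and high-risk groups respectively.

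**The concern.** Risk group belongs in the model because randomisation is stratified on it. As a predictor, though, it is coarse: the two planning means differ by only 4.45 hours, against standard deviations of 29.5 and 40.06 hours. Nearly all the variation in HFNC duration is left in the residual. In infants under 12 months, age and weight might account for some of it, and both are on record.

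Precision matters here for two reasons. The hypothesis stated under Background Information is that the arms do not differ, and a null result tells the reader only as much as its confidence interval allows. The Objectives also call for a comparison of the feeding routes in the high-risk group against the low-risk group, and each group was sized for only about 80% power.

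**Working it through.** **Inputs.** From the Statistics section: difference 24 h; SD 29.5 h (low risk) and 40.06 h (high risk); means 83.3 and 87.75 h; N 48 and 88; and "Assuming B of 0.8 and alpha of 0.05", with the 0.8 read as power. Equal allocation comes from Data and Safety Monitoring ("Because this is a randomized control trial with equal groups"). Sidedness is not stated. The R-squared of age and weight is not given, so a range of 0 to 0.30 is assumed.

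**Step 1: reproduce the plan's N.** Per arm, n = 2(1.960 + 0.842)² SD² / 24², two-sided.
- Low risk: 2 × 7.849 × 870.25 / 576 = 23.7, so 24 per arm, total 48.
- High risk: 2 × 7.849 × 1604.80 / 576 = 43.7, so 44 per arm, total 88.

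Both match. A one-sided test would give 38 and 70, so the plan's figures are two-sided and use no covariate adjustment. Power at these N is 80.5% and 80.2% (78.8% and 79.3% with the t distribution).

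**Step 2: variance explained by risk group.**
- Pooled within-stratum variance = (46 × 29.5² + 86 × 40.06²) / 132 = 1,348.8, so the SD is 36.7 h.
- Between-stratum variance = (48/136)(88/136)(4.45)² = 4.52.
- Share explained = 4.52 / (4.52 + 1,348.8) = 0.0033, about 0.3%.

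**Step 3: effect of adjustment, assuming a linear model.** Here R² is the share of within-stratum variance that the added covariates explain. The SE is multiplied by √(1 − R²). The pooled SE without them is 36.7 × √(4/136) = 6.30 h. The equivalent unadjusted N is 136/(1 − R²).

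| Assumed R² | Change in SE | Pooled SE (h) | 95% CI half-width (h) | Power, low risk (N=48) | Power, high risk (N=88) | Equivalent N |
|---|---|---|---|---|---|---|
| 0 | 0 | 6.30 | 12.3 | 80.5% | 80.2% | 136 |
| 0.05 | −2.5% | 6.14 | 12.0 | 82.4% | 82.2% | 143 |
| 0.10 | −5.1% | 5.98 | 11.7 | 84.4% | 84.2% | 151 |
| 0.20 | −10.6% | 5.63 | 11.0 | 88.3% | 88.1% | 170 |
| 0.30 | −16.3% | 5.27 | 10.3 | 92.1% | 91.9% | 194 |

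The table does not deduct the price of the extra terms, which is step 4.

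**Step 4: the price if the covariates are useless.** With p coefficients already in the model, two non-prognostic covariates inflate the variance by approximately (N − p − 1)/(N − p − 3).
- N=136, p=3: 132/130, a rise of 1.5%.
- N=88, p=2: 85/83, a rise of 2.4%.
- N=48, p=2: 45/43, a rise of 4.7%.

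The break-even R² is one minus the reciprocal of each ratio: about 0.015, 0.02 and 0.04.

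**Step 5: power of the pooled model as it stands.** 24/6.30 = 3.81, and 3.81 − 1.96 = 1.85, which gives about 97% power for 24 h without age or weight.

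**The case against.** The strongest reply is that nothing in the plan is wrong. Adjusting for the stratification factor is a prespecified analysis that matches the randomisation. The stated N holds without further covariates, and the pooled model already has about 97% power for 24 hours. At R² 0.10 the pooled interval narrows by only about 0.6 h on each side. Prematurity is already part of the risk-group definition, and the SAP acknowledges limited precision by adding Bayesian analyses. All of this stands, and it sets the weight of the point: an optional gain rather than a defect.

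A reader might infer that the comparison is shown to be imprecise because age and weight are left out. The documents do not support that. They report the retrospective data only as means and SDs, and give no relation of age or weight to HFNC duration. The gain could be nil.

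A reader might also infer that unadjusted chance imbalance in age or weight makes the result invalid. It does not: under randomisation, the standard error and p-value already allow for such imbalance.

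Nor is the change free. It uses up to two degrees of freedom and needs a rule for missing values, since the data come from chart review. Age and weight probably overlap in infants, so the second may add little. Finally, the √(1 − R²) rule is for a linear model and need not carry over to a time-to-event or other non-linear regression, which the SAP does not rule out.

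What survives the reply is that the downside is small and known, while the possible gain is larger and falls where the design has least to spare: the two strata, and the confidence interval around a hypothesis of no difference.

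**Conclusion.** The point holds as a conditional efficiency improvement. It is certain that the model adjusts only for risk group, that risk group explains about 0.3% of the variance on the planning figures, and that age and weight are collected but are not covariates. The size of the benefit is not known. It runs from a very small loss when the covariates predict nothing to a standard error about 16% smaller at R² 0.30. In the pooled analysis, any R² above about 0.015 repays the cost of two covariates.

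These figures assume a linear model, 1:1 allocation, full enrolment of 136, the planning SDs, a single pooled residual variance although the strata SDs differ, and the same R² in both strata. They do not show that the planned conclusion is at risk.

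**What to change.** Before any outcome data are seen, state the primary model in the SAP as treatment + risk group + age at randomisation (continuous). Add weight at study entry (continuous) only if the retrospective admissions data used for the sample size show that it contributes beyond age. If those data do not hold weight, use age alone. Say whether the regression is linear, and whether the same covariates are used when the strata are analysed separately.

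Add a simple rule for missing covariate values that does not depend on arm or outcome, for example replacement by the risk-group mean, so that every randomised infant stays in the analysis.

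The cost is a sentence or two in the SAP, one look at existing data, and one or two degrees of freedom. No new patients or measurements are needed.
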